
Study 2 Baseline and Randomization: The web-based screening survey will automatically generate an eligibility determination. Students who are ineligible will be shown a message thanking them for their interest in the study and directing them to campus resources that are available to them if they wish to discuss AOD issues. Those meeting the eligibility criteria above will automatically be directed to complete the baseline assessment measures. Once baseline is completed, students will be randomly assigned to either an intervention group (PFI) or assessment only control (AOC) group. Those in the intervention will immediately receive online personalized feedback (see below) on their PSM misuse, academics, and links to alternatives. Over the course of the quarter/semester, students in the intervention group will receive a link to view 4 additional modules surrounding PSM misuse, AOD use, Consequences, and Beliefs/Motives about PSM use. The AOC group will receive a "thank you" screen providing referrals/emergency numbers. Students will be assessed at 6, 12 and 18 months post-baseline using similar email invitations and reminders (expected retention 90% based on past research). Participants will be paid \$20, \$25, and \$30 for each follow-up survey. Students who indicate significant alcohol or drug dependence will be contacted and referred (See Human Subjects). We will make any indicated adjustments/refinements to feedback based on findings prior to *Study 3*.

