We will then examine effects on PSM, marijuana, and alcohol use and consequences. These outcomes are integers, bounded at zero, and often times positively skewed. Because of potential violations of regression assumptions that can arise due to the non-normal distribution, we will use a generalized form of the linear mixed model (GLMM) with a Poisson distribution in order to more appropriately model these outcomes as counts¹¹⁷. Count regression coefficients are connected to the outcome via a natural log link and are commonly exponentiated (e^β) to yield rate ratios (RRs) describing the proportional increase in the outcome for a 1-unit increase in the predictor (e.g., Treatment (1) compared to Control (0)).

To assess mediation hypotheses, we will utilize an approach that has been used by co-investigators with similar data to the proposed study¹⁹⁷. Kenny et al.¹⁹⁸ described mediation using multilevel models for longitudinal treatment data similar to the present data. Specifically, Kenny et al. focused on change in the direct treatment pathways from a model without the mediator to a model with the mediator (i.e., the common c and c' pathways in the mediation literature). In the present context, that is the treatment cross-level interactions with time ($\beta_{11} - \beta_{41}$) for the model presented above compared to one in which mediators are included as Level 1 time-varying covariates. We will use this approach and consider the percent reduction in effects after the mediator is included in the model. In Neighbors et al¹⁹⁹, this approach was extended using a nonparametric bootstrap¹⁹⁹ to allow estimation of the indirect path without making normality assumptions on the sampling distribution of the indirect effect. Perceived benefits and norms of PSM, use of alternative strategies, and alcohol and marijuana use will be included as the Level 1 time-varying mediators of interest and PSM use and consequences will be modeled as the outcomes. To assess moderators of efficacy, we will include level 2 covariates for baseline levels of motivations of PSM and demographic characteristics as well as their interactions with treatment in the GLMM.

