Aim 3: Efficacy of in-person and web-based interventions. GLMM Poisson regression will be also used to test the efficacy of the web-based PFI and in-person MI on reducing PSM use and consequences. Using the basic model equation, dummy variables rather than a single treatment indicator will be included as Level 2 covariates for web-based PFI and in-person MI such that the reference will be the control group. In addition to comparisons of the two intervention groups to the control, we will also conduct post-estimation general linear contrasts to compare effects of the web-based PFI and in-person MI on the PSM outcomes.

Missing data and attrition. Our prior research has been successful at retaining participants with 85-93% retention over 6 months or longer. GLMMs provide unbiased estimates in the presence of missing data as long as it can be considered ignorable. Missing data are ignorable if they are either missing completely at random or missing at random after accounting for measured variables in analysis, including outcome at earlier time

points¹²⁰. As seen in previous studies, little efficiency is lost in GLMMs with 10%-20% missing data.

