Power. Because count outcomes will typically require a larger sample size to detect effects than continuous outcomes, we assess power for the GLMMs for PSM use. Thus, power estimates for the GLMM will be conservative for the linear mixed models. For Aim 2, we are not aware of power analysis software to estimate power for GLMMs; thus, we used a simulation-based approach. Simulations based on models that contain “true” effects can provide an estimate of power. Two-hundred datasets were generated based on the model in equation 1 where estimates for fixed and random-effects were guided by previously collected data of similar interventions for reducing problem alcohol use and the existing literature. The GLMM model was fit to each dataset and specific output were saved (e.g., regression coefficients, *p*-values). The percentage of datasets with statistically significant effects (i.e., $p < .05$) for a given hypothesis provides a simulation-based estimate of power for this hypothesis. A number of simulation runs were conducted varying the size of the fixed-effects. These simulations revealed a sample size of 600 per treatment condition will yield power > 0.80 given the magnitude of the treatment \times time-dummy interaction coefficient was $-.13$ or smaller. Assuming no baseline differences in the outcome, this would correspond to a rate ratio of $.87$ at a given follow-up time point (i.e., a 13% decrease in PSM use for PNF intervention compared to control). Given our power to detect fairly small effects of the Aim 2 intervention, we would expect reasonable power to detect mediated and moderated effects as well. For Study 3 planned analyses of the web-based and in-person interventions, we also ran similar sets of simulations to assess power for varying effect sizes. We used similar estimates of random effects, but allowed the fixed effect of the intercept to be higher given the high risk sample and we specified a sample size of 100 per arm (300 total). Based on the simulations, we would expect power of $.80$ or higher to detect coefficients $-.3$ or smaller which corresponds to a RR of $.74$.

Timeline:

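### The Study 2 power statement misconverts its detectable effect as printed (-.13 is RR .88, not .87) and shows no allowance for the 10% loss the plan expects

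*Combined protocol and SAP*

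**What the plan says.** The Power section of the combined protocol and SAP reports a simulation of 200 datasets generated from the Aim 2 model. It states that "a sample size of 600 per treatment condition will yield power > 0.80", provided the treatment-by-visit "interaction coefficient was $-.13$ or smaller". It then says that, with no baseline difference, "this would correspond to a rate ratio of $.87$ at a given follow-up time point", which it describes as "a 13% decrease in PSM use for PNF intervention compared to control". Power is the share of datasets with "statistically significant effects (i.e., $p < .05"). The numerical fixed and random effects are not given, and missing outcomes are not mentioned.

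Three other places bear on this:

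- **Aim 2, count outcomes:** "Count regression coefficients are connected to the outcome via a natural log link and are commonly exponentiated" to give rate ratios. This fixes the conversion rule.
- **Aim 2, model:** 1,200 people in total, which is 600 per condition. The primary coefficients compare the conditions on change from baseline to each single follow-up visit.
- **Retention:** Study 2 Baseline and Randomization gives "expected retention 90% based on past research". Missing data and attrition cites 85-93% retention in earlier work and says that "little efficiency is lost in GLMMs with 10%-20% missing data".

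For Study 3 (100 per arm), the Power section gives power of .80 or higher for a coefficient of -.3, converted to RR .74.

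**The concern.** Two things in the headline power claim do not fit the rest of the plan. First, the printed coefficient and the printed rate ratio do not satisfy the plan's own rule. The figures .87 and 13% are what one gets by subtracting .13 from 1 rather than exponentiating, whereas the Study 3 figure is exponentiated correctly.

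Second, the sample size in the power statement equals planned enrolment. A tenth of participants are expected to be lost, and each primary coefficient is a contrast at one visit, so someone who misses that visit contributes little direct information to it. The sentence on efficiency in the missing-data section carries no figure for this contrast.

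At stake is how the smallest detectable effect of the main trial is read. The Power section also leans on this claim when it expects reasonable power for mediation and moderation.

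**Working it through.** **1. The conversion.** Inputs: coefficient -.13, RR .87 and 13% (Power); RR = e^β (Aim 2).

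- exp(-.13) = .878, so the decrease is 1 - .878 = 12.2%. To two decimals this is RR .88 and 12%. The plan's figure is not reproduced.
- In reverse, ln(.87) = -.139.
- Linear shortcut: 1 - .13 = .87, which matches the printed figure exactly.
- Rounding: exp(-.1335) = .8750 and exp(-.135) = .8737. A coefficient between about -.1335 and -.135 would therefore print as -.13 and give an RR printed as .87. For example, exp(-.134) = .8746, a decrease of 12.5%, printed as 13%.
- Study 3: exp(-.3) = .741, which agrees with the stated .74.

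**2. Enrolment against retention.** 1,200 / 2 = 600 per condition, the number in the power statement. At 90% retention, 600 × .9 = 540 per condition have an outcome at a given visit; at 80%, 480.

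**3. Effect of the loss on power.** The plan's power cannot be reproduced, because the intercept, time effects and random-effect variance are not given. As assumptions, take two-sided α = .05, full-data power of exactly .80 at -.13, and a normal approximation. The standardised effect is then 1.960 + 0.842 = 2.802.

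(a) Complete-case, the pessimistic end: the standardised effect is multiplied by √r, where r is retention.
- r = .9: Φ(2.802 × √.9 - 1.960) = .757
- r = .8: Φ(2.802 × √.8 - 1.960) = .707

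(b) Baseline data kept, as in the planned mixed model: assume a Poisson random-intercept model with equal expected counts over time apart from the treatment effect. The variance of the coefficient is then proportional to 2 + (1 + 1/RR)/r. With RR = .878, 1/RR = 1.139.
- Full data: 2 + 2.139 = 4.139
- r = .9: 2 + 2.139/.9 = 4.376. Ratio 1.057, square root 1.028. Power = Φ(2.802/1.028 - 1.960) = .778
- r = .8: 2 + 2.139/.8 = 4.673. Ratio 1.129, square root 1.063. Power = Φ(2.802/1.063 - 1.960) = .751

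| Retention | Power, complete-case | Power, baseline kept | Coefficient for 80% power (RR), complete-case | Coefficient for 80% power (RR), baseline kept |
|---|---|---|---|---|
| 90% | .757 | .778 | -.13/√.9 = -.137 (.872) | -.13 × 1.028 = -.134 (.875) |
| 80% | .707 | .751 | -.13/√.8 = -.145 (.865) | -.13 × 1.063 = -.138 (.871) |

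**4. Full-data power needed to keep .80 at 90% retention.**
- Complete-case: Φ(2.802/√.9 - 1.960) = .840
- Baseline kept: Φ(2.802 × 1.028 - 1.960) = .821

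**5. Precision of the simulation.** With 200 datasets and power near .80, the Monte Carlo standard error is √(.8 × .2/200) = .028, or 2.8 points.

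**6. Study 3, on the same anchor, taking 90% retention for illustration.** Complete-case: -.3/√.9 = -.316, RR .73. The same direction of change applies.

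**The case against.** The strongest reply is that little turns on this. The gap in RR is .878 - .870 = .008, and two-decimal rounding of a coefficient near -.134 would remove it. The stated power is only a lower bound: if full-data power were about .84, even a complete-case analysis at 540 per arm would reach .80. The mixed model keeps every observed visit, and baseline is completed before randomisation, so a complete-case calculation overstates the loss. Attrition is also addressed: the plan cites earlier retention, states the ignorability assumption and argues that the efficiency loss is small. A loss of 2 to 4 points is about the size of the simulation's own standard error.

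Much of this stands, and it rules out three stronger readings that a reader might infer:

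- **That the plan powers on 600 complete cases.** The text gives only a sample size per condition. It does not say whether missingness was simulated.
- **That power above .80 is not delivered.** With a lower bound and no simulation inputs, this cannot be shown.
- **That coefficient, rate ratio and power all contradict each other.** Only the printed coefficient and rate ratio disagree, and rounding may explain even that.

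What the reply does not remove is narrower. The Power section says the runs varied the size of the fixed effects, so the coefficient was a chosen input, for which a round -.13 is the more natural reading. The efficiency sentence gives no number for a single-visit contrast. And a simulation with a standard error of 2.8 points cannot tell a full-data power of .80 from one of .82 to .84, which is the distinction that matters here.

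**Conclusion.** The point holds, and it is minor. As printed, the Study 2 detectable effect is misconverted: -.13 is RR .88, a 12% decrease, unless the true input was an unprinted value near -.134. The power claim also shows no allowance for the plan's expected 10% loss. On the assumption that full-data power is exactly .80, that loss costs about 2 to 4 points (power .76 to .78); at 80% retention the cost is about 5 to 9 points (.71 to .75). These figures further assume a two-sided 5% test, a normal approximation and, for the upper end of each range, equal expected counts over time. The finding is that adequate power at the expected retention has not been shown, not that it is absent.

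**What to change.** - In the Power section, change RR .87 and 13% to RR .88 and 12%, or print the unrounded coefficient if that is the source of .87.
- Re-run the Study 2 and Study 3 simulations with 10% and 20% of outcomes missing per visit and more than 200 datasets. State the fixed and random effects used and whether the test is two-sided.
- Restate the detectable coefficient and rate ratio at 80% power for each study, to three decimals. On the assumptions above, Study 2 at 90% retention should come out at about -.134 to -.137, RR .87 to two decimals.
- In Missing data and attrition, replace the general efficiency statement with the simulated loss for the visit-specific coefficients.

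The cost is a simulation re-run and a few edited sentences. No extra participants are needed, and the design and analysis do not change. The only downside is that the stated figure may become slightly less favourable.

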Web-Delivered Intervention. Derivatives of BASICS such as Web-based PFIs have been efficacious in reducing college student drinking⁵⁸⁻⁶². Personalized normative feedback (PNF) interventions for college student alcohol use⁶⁷⁻⁶⁸, which focus primarily on correcting misperceived descriptive norms by providing accurate normative feedback, have evolved from BASICS and resulted in significant effects on drinking⁹³⁻⁹⁶. There is reason to believe normative feedback may have a similar impact on PSM misuse given recent data suggesting widespread normative misperceptions for PSM¹⁵⁶. Thus, **Study 1** aims to document accurate norms on each of the three participating campuses, in order to adapt normative feedback components of a PFI for PSM misuse. Consistent with preliminary research, we hypothesize that students' perceived norms of PSM will be greater than actual norms and these normative perceptions will relate to student's own PSM.

Costs associated with personalizing information via the Web are quite low, suggesting wide potential reach and resultant public health benefit of even modest improvements^{42, 43, 45}. Internet-delivered tailored prevention or intervention materials have targeted a range of health behaviors with a variety of populations⁴², including tobacco use^{43-44, 47-52}, depression and anxiety⁵³⁻⁵⁷, and drinking⁵⁸⁻⁶². Web approaches are attractive in a stepped care model due to cost-effectiveness, personalization, and widespread accessibility of the internet⁴²⁻⁴⁴. This approach may be ideal for students, as younger individuals not only wish to access health information through technology, but are critical of more traditional methods⁴⁶. Thus, **Study 2** aims to reach college students who engage in PSM misuse through web screening and intervention⁴². We hypothesize that participants who receive the PFI will reduce PSM misuse assessed at follow-ups. We further expect reductions in perceived benefits of PSM and perceived descriptive norms for PSM, and increases in use of alternative behaviors to support academic success, and expect these changes will mediate impacts on PSM use at follow-ups. We

further expect secondary effects of the intervention on alcohol and marijuana use, and expect these reductions will partially mediate PSM outcomes (see Mediators below). Finally, we will explore PSM motives and demographics as potential moderators of intervention efficacy (see Moderators below).

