Moderators: Motives for PSM misuse and Demographics. Evidence suggests students misuse prescription stimulants for a variety of reasons^{91-92, 159, 177}. Understanding motives for PSM misuse is important to identify necessary intervention components and to determine for whom interventions are most useful. Motivational models of substance use suggest behavior is motivated by different reasons, leading to theoretically and psychologically distinct behaviors^{195, 196}. Different motivations are associated with unique patterns of use and consequences, influencing when or where one will use a substance, how frequently or how much one will use, and what consequences may occur^{195, 196}. Studies of PSM use through alternative assessment methods (e.g., Twitter and Wastewater analysis)¹⁸²⁻¹⁸⁴ have confirmed that PSM use among students peaks around mid-terms and finals, supporting that perceptions of academic benefit and academic motives lead to PSM misuse among students. Indeed, self-reported motives for use among students include improving concentration, to help with studying, enhance academic performance, and, with less frequency, to counteract effects of other drugs, lose weight, experiment, and/or get high^{1, 3, 29, 91-92, 159, 177}. Overall, reasons for PSM misuse have been characterized into three main categories: academic motives, partying motives, and both academic and partying motives. The proposed intervention addresses each of these motives for PSM misuse. Students who engage in PSM misuse for academic reasons may benefit differently from those who use it more for recreational reasons. Each kind of user may benefit from alternative strategies to achieve desired academic and/or social outcomes rather than relying on PSM. Thus, the current study will explore whether student’s motives for PSM misuse will moderate intervention efficacy. We will also explore whether characteristics including gender, race/ethnicity, and fraternity/sorority status moderate intervention effects.

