Aim 1: To examine whether perceived norms of PSM differs from the “actual” prevalence as estimated by the screening sample, the actual prevalence will be subtracted from the perceived prevalence. A one-sample t-test will be used to assess whether the difference score is statistically significantly greater than 0. If the difference score is a non-normal distribution, we will instead use a non-parametric Wilcoxon sign rank test.

Aim 2: Evaluate efficacy of interventions. We will first examine effects of the intervention on perceived norms, benefits of PSM, and use of alternative strategies as separate outcomes using linear mixed models (a.k.a. hierarchical linear or multilevel models¹²⁰). This project will have 5 repeated measures, yielding up to 6,000 Level 1 observations (repeated-measures) across 1,200 Level 2 (people). The following equation represents a basic analytic model for Aims 2 and 3:

$$\text{Level 1: } Y_{ti} = \pi_{0i} + \pi_{1i}(\text{Post})_i + \pi_{2i}(\text{Month6})_i + \pi_{3i}(\text{Month12})_i + \pi_{4i}(\text{Month18})_i$$

$$\text{Level 2: } \pi_{0i} = \beta_{00} + \beta_{01}(\text{Tx})_i + \beta_{02}(\text{Site})_i + r_{00i}$$

$$\pi_{1i} = \beta_{10} + \beta_{11}(\text{Tx})_i + \beta_{12}(\text{Site})_i$$

$$\pi_{2i} = \beta_{20} + \beta_{21}(\text{Tx})_i + \beta_{22}(\text{Site})_i$$

$$\pi_{3i} = \beta_{30} + \beta_{31}(\text{Tx})_i + \beta_{32}(\text{Site})_i$$

$$\pi_{4i} = \beta_{40} + \beta_{41}(\text{Tx})_i + \beta_{42}(\text{Site})_i$$

where *Post*, *Month6*, *Month12*, and *Month18* are dummy codes for follow-up visit such that the reference time point is baseline; *Tx* represents randomly assigned treatment condition; *Site* represents the study site; *i* indexes participants; *r_{00i}* represents a random effect for the intercept; and *Y_{ti}* represents the outcome for each individual, *i*, at each time, *t*. $\beta_{11} - \beta_{41}$ are primary coefficients as they compare treatment conditions for the difference in the outcomes from baseline to each of the follow-up visits. The model assumes conditional independence, given random-effects and (multivariate) normality of Level 2 random-effects. As additional analyses, we will also specify time as a continuous variable in order to assess differences between intervention and control groups in slopes over time.

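### Power above .80 for a Study 2 main effect of -.13 does not carry over to moderated effects: an evenly split binary moderator needs a difference of about -.26

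*Combined protocol and SAP*

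**What the plan says.** The Power section describes 200 simulated datasets per run, generated from the basic model in Data Analysis, Aim 2. It reports: "These simulations revealed a sample size of 600 per treatment condition will yield power > 0.80" when the interaction of treatment with a follow-up dummy is -.13 or more negative, which it translates to a rate ratio of .87.

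The next step is verbal: "Given our power to detect fairly small effects of the Aim 2 intervention", it continues, "we would expect reasonable power to detect mediated and moderated effects as well". It gives no size of moderated effect, no moderator prevalence, no power value and no moderator simulation.

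In the basic model the Level 2 predictors are treatment and site only. The treatment terms on the follow-up dummies "are primary coefficients as they compare treatment conditions for the difference in the outcomes from baseline to each of the follow-up visits". For moderation, Aim 2 adds "level 2 covariates for baseline levels of motivations of PSM and demographic characteristics as well as their interactions with treatment in the GLMM".

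The background calls this work exploratory. Under Web-Delivered Intervention: "we will explore PSM motives and demographics as potential moderators of intervention efficacy". The Moderators section names motives, gender, race/ethnicity and fraternity/sorority status. It says that understanding motives matters in part "to determine for whom interventions are most useful".

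**The concern.** A main effect uses all 1,200 participants to estimate one treatment contrast. A moderator test estimates that contrast separately in subgroups and compares the results, so it is less precise. Good power for a small main effect therefore says little about power for a difference of similar size between subgroups.

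What is at stake is how null moderator results are read. Someone who relies on the Power section could take a non-significant interaction with, say, gender as evidence that the feedback intervention works equally well in both groups. If power for a moderate difference is near .3, such a result is uninformative.

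**Working it through.** **Inputs from the Power section.** 600 per arm, power above .80, coefficient -.13, p < .05. Sidedness is not stated; I take two-sided. Because the section gives only a lower bound on power, I take exactly .80 and then vary it.

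**The plan's own figure.** It cannot be reproduced independently, because the intercept and random-effect variance used in the simulation are not given. The standard error it implies can be recovered:

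- z = 1.960 + 0.842 = 2.802
- SE(main) = .13 / 2.802 = .0464

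A plausibility check uses the Study 3 figure. Scaling from 600 to 100 per arm gives .13 x sqrt(6) = .318. The plan states -.3 with a higher intercept, so the two figures are consistent.

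**Interaction standard error.** If the two levels of a binary moderator hold shares q and 1 - q of the statistical information, SE(interaction) = k x SE(main), with k = 1/sqrt(q(1 - q)). The minimum is k = 2, at q = .5. With similar event rates, q is the share of participants. The multiplier does not need the missing variance inputs.

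Detectable difference at .80 power = k x .13. Power at -.13 = Phi(2.802/k - 1.960), plus a negligible lower tail.

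| Moderator | k | Detectable at .80 | Ratio of rate ratios | Power at -.13 |
|---|---|---|---|---|
| Binary 50/50 | 2.00 | -.260 | .77 | .29 |
| Binary 20/80 | 2.50 | -.325 | .72 | .20 |
| Continuous, per SD | 1.00 | -.130 | .88 | .80 |

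**If main-effect power exceeds .80.** At .90 (z = 3.242), 50/50 power at -.13 is Phi(3.242/2 - 1.960) = .37, and 20/80 power is .25. For the 50/50 interaction to reach .50, the main-effect z must be 2 x 1.96 = 3.92, which is main-effect power of Phi(1.96) = .975.

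**If event rates differ between subgroups (rates assumed).**

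- 20/80, smaller group at 1.5 times the rate: q = .30/1.10 = .273, k = 2.24, detectable about -.29.
- 20/80, smaller group at twice the rate: q = .40/1.20 = .333, k = 2.12, detectable about -.28.
- 50/50, one half at twice the rate: q = 1/3, so k rises from 2.00 to 2.12.

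**If three follow-ups are averaged.** With a constant effect and a Poisson random-intercept approximation, the variance of a baseline-to-follow-up contrast changes by (1 + 1/3)/2 = .667, so the SE changes by .816. The 50/50 figure becomes .26 x .816 = .21, and power at -.13 becomes Phi(2.802/(2 x .816) - 1.960) = about .40. The main-effect figure also falls, to .13 x .816 = .11, so the ratio is still 2.

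**Simulation check.** These are random-intercept Poisson runs with one follow-up and a mean count chosen to give main-effect power of about .80. At a mean count of 3.3 (3,000 runs), 50/50 interaction power was .29 at -.13 and .81 at -.26. At 3.2 (4,000 runs) it was .286 and .791. The 20/80 case at -.325 gave .766, and the continuous case at -.13 per SD gave .778. The factor of 2 is confirmed; the third decimal of the other figures is not.

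**The case against.** The strongest reply is that moderation is exploratory, the sentence is hedged, and the plan never defines what power counts as reasonable or claims .80 for an interaction of -.13. All of that is true. A reader might infer that the plan promises such power; it does not. But the sentence offers main-effect power as the ground for expecting moderator power, and that step is unsupported whatever threshold is meant.

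The splits, the benchmark of -.13 and the reading of the interaction as three-way are mine. The three-way reading rests on the plan's naming of the treatment-by-time terms as its primary coefficients.

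Motives may well be analysed as a questionnaire score. The statement that "reasons for PSM misuse have been characterized into three main categories: academic motives, partying motives, and both academic and partying motives" is a literature summary, not an analysis rule. For a score, .80 power at about -.13 per SD is less discouraging. Gender, race/ethnicity and fraternity/sorority status are categorical, so the factor of at least 2 applies to any two-group comparison on them.

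The equal-rates assumption is doubtful for fraternity/sorority status: the preliminary studies report higher use among residents of those houses. That is why the 20/80 case is given as a range.

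With an average effect of -.13 and a 50/50 split, a difference of -.26 means rate ratios of 1.00 and .77, while -.13 means .94 and .82. It is tempting to say that .80 power is reached only if one half does not benefit at all, or that the smaller difference is always missed about 7 times in 10. Those statements hold only for a single follow-up contrast at main-effect power of .80. The plan has several follow-ups and does not confine moderation to one.

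Finally, the phrase about for whom interventions are most useful is background rationale for studying motives. It does not commit the plan to settling that question with these tests, and nowhere does the plan say that a null moderator test shows a uniform effect.

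**Conclusion.** The point stands for moderation in Study 2. The power inference is unsupported, and for two-group moderators the smallest detectable difference is at least about twice the main-effect figure. For one follow-up and a 50/50 split that is about -.26, with power of about .29 at -.13 (about .37 if main-effect power is .90). Uneven splits generally need more: roughly -.28 to -.33 at 20/80, depending on relative event rates.

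The factor of 2 is robust. The absolute values are approximate, because they rest on a standard error recovered from a stated lower bound on power and on the assumptions above. The expected 90% retention is not mentioned in the Power section. If the simulation ignored it, both the main-effect and interaction figures worsen together.

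A reader might go further and conclude that Study 2 is underpowered, or that the mediation analyses are too. Neither follows: nothing here shows the main-effect power to be wrong, and mediation was not assessed. This is a defect in one power statement and in how null moderator results may be read.

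**What to change.** In the Power section, drop the inference from main-effect power to moderated effects and put in its place, for moderation, a statement to this effect:

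*For a binary moderator the smallest difference in treatment effect detectable with .80 power is at least about twice the main-effect figure: approximately -.26 (ratio of rate ratios about .77) at one follow-up for an even split, and larger for uneven splits. Moderator analyses are exploratory, and a non-significant moderator test does not show that the effect is uniform.*

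Label the figure approximate. Preferably, the sponsor's statisticians should confirm it by rerunning their existing simulation with a moderator term and their own intercept and variance inputs, for an even and an uneven split. If motives are analysed as a score, add the per-SD figure (about -.13) from the same run. The exploratory label already appears in the background sections and only needs to be carried over.

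The cost is a less favourable sentence and, if chosen, one more set of simulation runs. Sample size, data collection and analysis model do not change.
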